6.1. Study Population

6.1.1. Inclusion Criteria

- History of moderate to severe TBI based on worst GCS score within first 48 hours of injury (acceptable GCS range = 3-12)
- Age 22-60
- At least 24 months from date of onset
- Fluent in English and able to independently provide consent
- Retains decision-making capacity and is able to function independently (i.e., unsupervised) in the home setting
- Multiple unsuccessful attempts to sustain competitive employment or complete an academic degree-granting program of study

- Either receives no CNS stimulants or other medications known to affect cognitive function, or on stable doses of these medications for the last three months (see additional information regarding concomitant medications below)

6.1.2. Exclusion Criteria

- History of major developmental, neurologic, psychiatric or substance use disorder with evidence of disability prior to onset of TBI
- Major medical co-morbidities including: end stage renal failure, severe heart failure, severe congestive heart disease, coagulopathy severe respiratory problems, severe liver failure, uncontrolled hypertension or other significant medical co morbidities
- Have had a documented seizure within 3 months of study screening (subjects may re-screen if seizure free after initial screen failure)
- Malignancy with < 5 years life expectancy
- Untreated / uncontrolled (severe at the time of enrollment) depression or other psychiatric disorder
- Women of childbearing age who do not regularly use an accepted contraceptive method
- Inability to stop anticoagulation or platelet anti-aggregation therapy before, during and after surgery
- Previous DBS or other brain implants
- Previous ablative intracranial surgery
- Implantable hardware not compatible with MRI
- Condition requiring diathermy after DBS implantation
- Hardware, lesions or other factors limiting placement of electrodes in optimal target location in the judgment of the operating surgeon
- Concurrent enrollment in any other clinical trial
- Any condition or finding that, in the judgment of the PI, significantly increases risk or significantly reduces the likelihood of benefit from DBS

6.1.3. Concomitant Medications

Subjects who are on centrally-acting medications will remain eligible for enrollment as long as the dose of the medication has been stable for at least three months prior to the date of enrollment. All concomitant medication and concurrent therapies will be documented during the Baseline Visit, and at every subsequent study visit. At each study visit, the Study Coordinator will review and print the list of concomitant medications that were completed at the participant's prior visit in order to accurately review and document changes in the participant's concomitant medications or concurrent therapies. The generic name of the drug, presence/absence of the drug at the time of randomization, date started, dose, route, unit frequency of administration (i.e., schedule) and the date stopped or changed will be recorded. We will also record whether the medication was prescribed to treat an AE (and, if so, the date of the AE form) or a new clinical

problem that arose after enrollment. The same information will be recorded for non-pharmacologic therapies, with the exception of dose and route of administration.

If there are any changes in a centrally-acting medication, or if a new centrally-acting medication is added following randomization, the Study Coordinator will apprise the Sponsor and a protocol violation will be recorded. The Sponsor will evaluate the potential influence of the new medication on the study treatment and will make a disposition regarding continued participation in the trial. Any disposition recommending withdrawal from the trial will be reviewed by the Clinical Oversight Committee (see [Section 10](#) below) before any action is taken.

6.2. Informed Consent

If no exclusion criteria are identified during the pre-screening interview, the investigator/coordinator will provide the informed consent form ahead of time to potential candidates. Candidates will be asked to review and mark the document with questions. Study investigators will be available for questions in person or over the phone or teleconference. The coordinator will then arrange for a consent meeting with the sponsor to: (a) review the informed consent form; (b) clearly explain all study procedures, risks, potential benefits, alternative therapies (if available); and (c) answer any questions the participant may have regarding the study. The sponsor will be present for the entire informed consent meeting. A consent for release of medical records will be obtained during the consent meeting to acquire additional information and medical records related to study eligibility. The participant will be reminded that study eligibility will not be finalized until all screening and pre-operative tests and procedures have been completed.

After the study has been fully explained to the potential subject and all questions have been addressed, written informed consent will be obtained prior to the performance of any study-specific procedures. The method of obtaining and documenting the informed consent and the contents of the consent will comply with ICH-GCP and all applicable regulatory requirements, including local IRB requirements.

6.3. Randomization to Multiple Baseline Condition and Treatment Withdrawal

Following study enrollment, participants will be randomly assigned to 1 of 3 baseline conditions lasting 30, 44, or 58 days. Two participants will be assigned per condition. The staggered baseline schedule will enable assessment of CT-DBS effects within individual subjects and across subject pairs. Each participant will also be randomly assigned to a treatment withdrawal or continuation condition. Neither the investigator nor the participant will have knowledge or be apprised as to whether DBS is on or off during this period. For participants assigned to the treatment withdrawal condition, DBS will be switched off for 21 days (on days 170, 184, and 198 for cohorts 1-3, respectively) immediately after completing the 90-day unblinded treatment phase. Participants randomized to the continuation condition will continue to receive stimulation 12 hours per day over the same 21-day period. Upon conclusion of the 21-day treatment withdrawal phase, participants will undergo a final re-assessment on the multi-dimensional outcome assessment battery and on the electrophysiologic measures (on day 191, 205, or 219, depending on cohort). Currently there are no known safety issues related to withdrawing stimulation. The purpose of this follow-up visit is to determine if there is evidence of loss of effect in those assigned to the treatment withdrawal condition, and to evaluate the influence of

intervening factors on the effectiveness of DBS. The trial will be considered complete at the end of the treatment withdrawal phase.

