6. STUDY PLAN

The research plan is organized around the central aim of acquiring pilot clinical data that will inform the safety and efficacy of central thalamic-deep brain stimulation (CT-DBS) in the treatment of chronic cognitive impairment and residual disability caused by TBI. We intend to recruit 6 adults with a history of moderate to severe TBI (GCS = 3-12) who continue to demonstrate neuropsychological impairment and functional disability at least 24 months post-injury (Glasgow Outcome Scale- Extended = 5-7) {Wilson, 1998, Structured interviews for the Glasgow Outcome Scale and the extended Glasgow Outcome Scale: guidelines for their use}.

Following study enrollment, participants will be randomly assigned to 1 of 3 baseline conditions lasting 30, 44, or 58 days. Two participants will be assigned per condition. The staggered baseline schedule will enable assessment of CT-DBS effects within individual subjects and across subject pairs. Each participant will also be randomly assigned to a treatment withdrawal or continuation condition. This process is explained in detail in [Section 6.3](#) of this document.

Following a 30 to 60-day presurgical baseline phase to ensure surgical readiness and establish current level of function across multiple domains, participants will undergo implantation of a deep brain stimulator in the central lateral nucleus of the thalamus. Implantation of the stimulator will be followed by a staggered post-surgical baseline that will increase progressively for each pair of participants. After a 14-day stimulation titration phase, CT-DBS will be

administered for 90 consecutive days. Following the unblinded stimulation phase, participants will enter a 21-day double-blinded treatment withdrawal phase. The study will formally conclude at the end of the withdrawal phase. Participants will be given the option to continue to use the device following study termination, if they are receiving benefit.

The study design includes 3 unique features that were incorporated to detect treatment effects, reduce sources of bias and estimate generalizability:

- Subject pairs will be randomized to one of 3 progressively-increasing baseline observation periods. Should treatment be effective, improvements in performance on the outcome measures will occur in temporal contiguity to the onset of CT-DBS. This design element will help differentiate the effects of CT-DBS from random fluctuations in function.

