6.8. DBS Stimulation Titration/Optimization

On completion of the postsurgical washout phase (beginning day 66, 80, or 94, depending on cohort), DBS will be turned on for the first time to initiate the stimulation titration phase. During this phase, which will last 14 days for all participants, an array of stimulation parameters will be assessed to optimize the settings that will be used during the treatment phase. See [Appendix 1](#) to this protocol for the device programming SOP.

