6.11. Six Month Open Label Follow-Up Period

There will be a 6-month follow-up period at the end of the unblinded treatment phase. There will be two visits during this period with the visits occurring at months three and six. The month three follow up visit will be to assess general health, quality of life and to monitor battery supply

of the device. The six month follow up visit will be to assess general health, quality of life, neuropsychological status and to monitor battery supply of the device.

6.12. Unscheduled Visits:

Participants may have visits in between their regularly scheduled study visits if the sponsor-investigator deems necessary.

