9. ADVERSE EVENTS

9.1. Adverse Event Identification and Assessment

An adverse event is any undesirable clinical occurrence in a participant during the clinical investigation, having been absent at baseline (or, if present at baseline, appears to worsen), whether or not it is considered to be related to the device or to stimulation. The investigator will not be required to record transient stimulation-induced neurological effects (e.g., paresthesias) or findings within normal expected postoperative outcomes. For example, postoperative pain that is not outside expected levels will not be recorded as an adverse event. Postoperative events that involve a clinically significant severity of symptoms, duration of symptoms, or that require deviation from usual postoperative clinical interventions (e.g., pain lasting longer than expected and requiring long-term opioid use) will be recorded as adverse events. The testing of DBS in MCS subjects did not identify any adverse events that are specific to brain injured subjects.

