9.4. Anticipated & Unanticipated (UADEs) Adverse Device Effects

9.4.1. Anticipated Adverse Events

Those **known** adverse events and surgical interventions related to the device or procedure are extrapolated from a population of 299 patients who underwent DBS for movement disorders (Medtronic® DBS™ Therapy for Parkinson's Disease and Essential Tremor CLINICAL SUMMARY, 2013):

- Abnormal behavior
- Abnormal dreams
- Activities of daily living impaired
- Adverse drug reaction
- Agitation
- Akinesia
- Anemia
- Anxiety
- Aortic stenosis
- Appendicitis perforated
- Arteriosclerosis
- Arthralgia
- Arthritis
- Asthenia
- Asthma
- Back pain
- Balance disorder
- Benign prostatic hyperplasia
- Biopsy bone
- Bladder catheter removal
- Blood pressure increased
- Bone Fractures
- Bone graft
- Bradykinesia
- Breast cancer
- Bronchitis
- Burns third degree
- Cardiac pacemaker insertion
- Cartilage injury
- Cellulitis
- Cerebral haematoma
- Cerebral haemorrhage
- Cerebrovascular accident
- Chest discomfort
- Chest pain
- Cholelithiasis
- Clostridium difficile colitis
- Clostridium difficile sepsis
- Cognitive disorder
- Complication of device removal
- Confusional state
- Constipation
- Convulsion
- Cough
- Debridement
- Decubitis ulcer
- Deep vein thrombosis
- Deep vein thrombosis postoperative
- Dehydration
- Delirium
- Delusion
- Delusional disorder, persecutory type
- Depression
- Depression suicidal
- Device electrical finding
- Device failure
- Device migration
- Diabetic ketoacidosis
- Diverticulitis
- Dizziness
- Drooling
- Drug hypersensitivity
- Drug toxicity
- Dysgraphia
- Dyskinesia
- Dysphagia
- Dyspnoea
- Dystonia
- Dysuria
- Erectile dysfunction
- Fall
- Fatigue
- Freezing phenomenon
- Gait disturbance
- Gastric polyps
- Gastroduodenitis
- Gastrointestinal disorder
- Gastrooesophageal reflux disease
- Glioma
- Grand mal convulsion
- Haematoma
- Haemoglobin decreased
- Haemorrhage intracranial
- Hallucination
- Head injury
- Headache
- Hiatus hernia
- Hip arthroplasty
- Homelessness
- Hyperhidrosis
- Hyperkalaemia
- Hypertension
- Hypoaesthesia
- Hypotension
- Hypovolaemia
- Hypoxia
- Implant site erosion
- Implant site infection
- Implant site reaction
- Incision site complication
- Incision site pain
- Inguinal hernia
- Insomnia
- Intestinal obstruction
- Intestinal perforation
- Intraventricular haemorrhage
- Labile blood pressure
- Labile hypertension
- Lethargy
- Localized infection
- Lumbar spinal stenosis
- Lung neoplasm malignant

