10. CLINICAL OVERSIGHT COMMITTEE

It is the responsibility of the Sponsor-Investigator to oversee the safety of the study participants. This includes careful assessment and appropriate reporting of adverse events as noted above.

In addition, a Clinical Oversight Committee (COC) has been appointed to conduct ongoing reviews of the safety of the Study and make recommendations regarding changes to the risk/benefit of the Study, including recommendations to discontinue new patient enrollments or discontinue the Study. The COC will review all SAEs as they occur and will conduct routine reviews at least quarterly throughout the study.

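### The plan gives two incompatible ends of study and no end date for adverse-event collection, so it is unclear whether the six-month follow-up counts in the safety rate

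*Combined protocol and SAP*

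**What the plan says.** **The early end.** Section 6 says "The study will formally conclude at the end of the withdrawal phase" and places any later use of the device after study termination. Section 6.3 repeats the point ("The trial will be considered complete at the end of the treatment withdrawal phase") and puts the final re-assessment on day 191, 205 or 219.

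**The late end.** The synopsis gives a total duration of 12 to 14 months by cohort and lists the six-month open-label follow-up among the main study phases. Section 6.11 plans visits at months three and six. Of the first it says "The month three follow up visit will be to assess general health, quality of life and to monitor battery supply" of the device; the second adds neuropsychological status.

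**What hangs on the end of study.** Section 9.1 begins "An adverse event is any undesirable clinical occurrence in a participant during the clinical investigation". Under section 10 the Clinical Oversight Committee "will conduct routine reviews at least quarterly throughout the study". Section 9.5.4 covers deaths in the course of the study. The synopsis safety endpoint is a rate of AEs, serious adverse events (SAEs) and adverse device effects, with no observation period. Section 11 says only that AE data will be reported and tabulated.

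**The concern.** A rate needs a defined observation window. Here the window depends on when the study ends, and the protocol answers that in two ways. Two analysts following the same document could report different safety results from the same six participants.

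The period in doubt matters. The system stays implanted, and section 6.10 allows stimulation to continue where benefit is judged to be present. Section 9.4.1 lists harms that could occur then, including "Implant site erosion", implant site infection, device migration, device failure and suicidal ideation. Because these are listed as anticipated, the route for unanticipated adverse device effects (UADEs) in section 9.5.2 would not ordinarily pick them up. If collection stopped at the early end, the safety rate would be truncated. Implantation is also sequential: section 6.6.1 uses results from the first five patients to plan the sixth. Late events in earlier participants are therefore relevant to the committee.

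**Working it through.** **Inputs**
- First switch-on: "beginning day 66, 80, or 94, depending on cohort" (section 6.8).
- Titration: "During this phase, which will last 14 days for all participants" (section 6.8).
- Unblinded treatment: 90 days (section 6.9).
- Withdrawal or continuation: 21 days (section 6.3).
- Follow-up: six months. Section 6.11 starts it at the end of the unblinded phase; the synopsis lists it after the withdrawal/continuation randomization. Both starting points are tried.
- Month length: 30 days. The protocol defines a month this way only for the pre-surgical interval (section 6.5), so its use here is an assumption.

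**Step 1. Reproduce the plan's own days.** Switch-on + 14 + 90 = 170 / 184 / 198. Adding 21 gives 191 / 205 / 219. Both match section 6.3 in every cohort.

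**Step 2. Time inside the early end.** 14 + 90 + 21 = 125 days after switch-on in each cohort (191 − 66 = 205 − 80 = 219 − 94).

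**Step 3. Share of post-switch-on time after the early end.** Share = (end of follow-up − end of 21-day phase) / (end of follow-up − switch-on).
- Follow-up from the end of the unblinded phase: it ends on day 350 / 364 / 378. Outside: 180 − 21 = 159 days. Total: 125 + 159 = 284. Share: 159/284 = 56.0%.
- Follow-up from the end of the 21-day phase: it ends on day 371 / 385 / 399. Outside: 180 days. Total: 125 + 180 = 305. Share: 180/305 = 59.0%.
- With months of 28 to 30.44 days, the range over both starting points is 54.0% to 59.4%.

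**Step 4. Share of implanted time.** Erosion, migration and device failure run on the implant clock. The protocol gives no implant day. Subtracting the 30-, 44- and 58-day baselines from the switch-on days gives 66 − 30 = 80 − 44 = 94 − 58 = 36, so day 36 is assumed.

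| Cohort | Follow-up from end of unblinded phase | Follow-up from end of 21-day phase |
|---|---|---|
| 1 | 159/314 = 50.6% | 180/335 = 53.7% |
| 2 | 159/328 = 48.5% | 180/349 = 51.6% |
| 3 | 159/342 = 46.5% | 180/363 = 49.6% |

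Three of the six values are below half.

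**Step 5. Which end fits the stated duration?** At 30.44 days per month, days 191 to 219 are 6.3 to 7.2 months. Days 350 to 378 are 11.5 to 12.4 months, and days 371 to 399 are 12.2 to 13.1. The synopsis figure of 12 to 14 months can be approached only if follow-up counts as study time. On that reading the share outside is 0%.

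**The case against.** The best case against the concern is that the documents do place follow-up inside the study. The synopsis duration works only that way, and AE recording and committee review would then run to month six with nothing lost. This stands as one legitimate reading. It does not remove two explicit statements that the study ends earlier, and no section says which governs.

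A reader might infer from section 6.11 that AEs are not collected at the follow-up visits because they are not listed. That is weak evidence. The other visit and phase descriptions in section 6 do not itemise AE collection either; section 9 governs it. The declared end of study carries the point.

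A reader might also infer that follow-up harms could be reported nowhere. The documents do not support that. Section 9.5 records any adverse clinical event, and sections 9.5.1 and 9.5.2 set no time window for SAE and UADE reporting. Section 10 has the committee review all SAEs as they occur. Section 6.1.3 records at every study visit whether a medication was given for an AE, and both 6.11 visits assess general health. Events could surface by these routes. What is missing is a clear obligation to record and count them.

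Finally, days 191, 205 and 219 are participant days. With sequential implantation, one participant's completion does not end committee review while others are active. That narrows the committee part of the concern for earlier participants. It does not supply a collection window for each participant, and it does not help those who finish last.

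**Conclusion.** The point holds as a contradiction with consequences for the safety endpoint. Sections 6 and 6.3 end the study at day 191/205/219; the synopsis and section 6.11 carry it through a six-month follow-up; no AE collection end date is stated. If the early end governs, AEs in 56% or 59% of planned post-switch-on time need not be recorded or counted. The corresponding share of implanted time is about 47% to 54%. If the synopsis governs, the share is 0%.

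It would be too strong to say that most of the safety experience is lost. The share above one half depends on the early-end reading and on counting from switch-on; from an assumed implant day of 36 it is not always above half. The figures also assume 30-day months and describe planned elapsed days, not stimulation exposure, since continued stimulation depends on benefit. The plan gives no onset times for late hardware harms, so the number of events that might be missed cannot be stated.

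This should be corrected: the choice of reading changes what the safety rate measures, and the remedy is cheap.

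**What to change.** 1. Reconcile sections 6 and 6.3 with the synopsis and section 6.11, so that only the blinded comparison is complete at day 191/205/219. State from which day the six-month follow-up runs.
2. In sections 9.1 and 10, state that collection of AEs, SAEs and adverse device effects, and committee review, continue through each participant's month-six visit.
3. Add recording of AEs and device effects to both 6.11 visits.
4. In section 11, tabulate safety through month six, with the open-label period shown separately.
5. Section 9.5.3 gives no observation window and acts by terminating the trial. How it applies after day 191/205/219 is for the sponsor to reconcile with the other sections; no rule is proposed here.

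The cost is protocol wording, AE forms at two visits already planned, and possibly one or two more quarterly committee reviews. Reported AE counts may rise slightly.

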6.4. Screening Imaging

Following study enrollment but before the screening visit, participants will undergo volumetric MRI imaging including diffusion tensor imaging for surgical planning and to assess the degree of structural damage, which could preclude successful targeting of the DBS leads. Feasibility of successful targeting of the CT will be determined by the investigative team. If targeting is determined to be infeasible the subject will be withdrawn from the study.

